
### **1.5 Dose Rationale and Risk/Benefits**

The study will follow a 2x2 factorial design. Two supplements will be used: one will consist of 2 grams of a 3:2 ratio of EPA/DHA consumed orally (4 softgels=4g fish oil) once daily for 6 weeks and another will be 2000 IU daily of Vitamin D (1 capsule). The n-3 PUFA dose has been previously used for studies of other painful conditions and has been associated with a significant increase in the n-3 PUFA level and a reduction in the n-6:n-3 PUFA ratio over a 6 week period. The Vitamin D dose of 2000 IU per day has been previously used in other clinical trials, has been shown to correct Vitamin D to optimal levels, and has been shown to be safe. Participants in the comparator arm for n-3 PUFA will receive 4 grams of soybean/corn oil, which has been safely and effectively used as a comparator in a number of studies.

Chronic pain is associated with reduced mental and physical health and interferes with essential activities of daily life. Currently there are limited treatment options to address chronic pain once it has become established and the overarching aim of this clinical trial is to prevent chronic pain development, therefore there is a critical unmet need of safe, non-addictive, non-invasive preventative treatment options that can

be administered to burn survivors in the aftermath of injury. This study has the potential to benefit participants and future burn survivors and improve pain and general health outcomes. The risks of taking n-3 PUFAs and/or Vitamin D are small. Although n-3 PUFA preparations are well tolerated, potential side effects include fish like taste, belching, indigestion and GI upset, increased bleeding. Acceptance of this limited risk is reasonable based on the anticipated benefits to burn survivors at risk for chronic pain development. Side effects from Vitamin D are rare, however, it is possible that over supplementation of Vitamin D may be associated with headache, loss of appetite, dry mouth, metallic taste, and nausea/vomiting. **The risks to the subjects in experiencing these side effects is balanced against the potential for a new, safe, non-opioid preventative treatment option for chronic pain following MThBI.**

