**Secondary Objectives:**

[figure not shown]
1. To demonstrate potential efficacy of n-3 PUFAs/Vitamin D on decreasing graft site pain severity in survivors of MThBI requiring surgery. This will provide data on the confidence interval around our model estimates, which will inform a larger clinical trial.
2. Demonstrate the potential efficacy of n-3 PUFAs/Vitamin D on reducing pain interference on important domains of life function measured by the Brief Pain Inventory and SF-12 Mental and Physical Component Scores.
3. To demonstrate the utility of a clinical prediction tool based on a logistic function derived from a previous observational cohort study to enhance enrollment of a population of MThBI survivors at greater risk of chronic pain development.
4. To explore sex as a biological variable to determine whether there are differences in safety and efficacy among women and men.

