### **3.4 Secondary Study Endpoints**

Several secondary endpoints will be included in this study. The efficacy of n-3 PUFA/Vitamin D to improve overall mental and physical health (SF-12 mental and physical component scores), pain interference, depression, anxiety, and stress, and opioid consumption will be assessed. Therapeutic response to Vitamin D and n-3 PUFA will be assessed in both women and men.

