**Primary study measures by timepoint.**

Domain	Measure	D1	6W	3M	6M	1Y
Demographic information	Age, sex, ethnicity, education level, income level, marital status	•				
Pre-burn psychological traits	Pain catastrophizing, SF12 MCS, DASS21, Life events checklist	•				
Burn Injury Characteristics	Estimated % TBSA, mechanism of burn, donor/graft site location	•				
Graft Site Pain severity	0-10 numeric rating scale; Brief Pain Inventory, DN-4, S-LANSS  †RPS	•	•	•	•	•
Physical function	SF12, work/disability questions	•	•	•	•	•
Depressive Symptoms	Depression anxiety stress scale (DASS21)	•	•	•	•	•
PTSD symptoms	PTSD Symptom Severity index-interview	•	•	•	•	•
Somatic Symptoms	Somatic symptoms inventory	•	•	•	•	•
Alcohol and drug use	TWEAK/SAOM		•	•		•
Burn wound evaluation	Digital photos of injury/wound site	•	•	•	•	•
Dissociative Symptoms	Michigan Critical Events Perception Scale	•				
Analgesic Medication Use	Daily milligram morphine equivalents, non-opioid analgesic use	•	•	•	•	•

†RPS = Regional pain scale, M=month, W=week, D= day, PTSD=post-traumatic stress disorder, TBSA: total body surface area, DN-4 Douleur Neuropathique 4, neuropathic pain questionnaire, S-LANSS: self report version of the Leeds Assessment of Neuropathic Pain scale SF-12: 12 item short form from the medical outcomes survey.

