#### **Secondary Analyses:**

Similar models as for the primary outcome will be fit for both the Brief Pain Inventory and the SF-12 Mental and Physical Component Scale Scores.

**Sex as a biological variable (SABV)** will be examined in treatment response including sex-by treatment interaction terms in the mixed effect model specified above and exploring sex differences in therapeutic response to Vitamin D and n-3 PUFAs.

**General mental and physical health** will be assessed using SF-12 physical and mental component scores (PCS and MCS) and the impact on physical and mental functioning will be determined in each of the treatment groups. A clinically important reduction in SF-12 PCS and MCS ranges between 2.5-4.5; therefore, a reduction of  $\geq 4.5$  will be considered a clinically significant improvement MCS/PCS.

**Brief Pain Inventory:** We will also use multivariable analysis to determine the role of n-3 PUFA/Vitamin D supplementation in pain interference using composite and individual measures of the Brief Pain Inventory.

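### The SF-12 clinical-importance rule runs the wrong way: a fall of 4.5 points or more in a health score is called an improvement

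*Combined protocol and SAP*

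**What the plan says.** The rule is in section 6.2, Secondary Analyses, in the paragraph on general mental and physical health. The outcome there "will be assessed using SF-12 physical and mental component scores (PCS and MCS"). The paragraph continues: "A clinically important reduction in SF-12 PCS and MCS ranges between 2.5-4.5", citing a published source. It concludes that a reduction of at least 4.5 "will be considered a clinically significant improvement MCS/PCS". The word *reduction* thus appears both in the premise and in the operative rule.

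Other parts of the protocol bear on the direction of benefit:

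- Section 1.5: "Chronic pain is associated with reduced mental and physical health".
- Section 3.4: a secondary endpoint is efficacy to "improve overall mental and physical health (SF-12 mental and physical component scores").
- Section 2, second secondary objective: "reducing pain interference on important domains of life function measured by the Brief Pain Inventory and SF-12 Mental and Physical Component Scores".

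The table of measures in section 5.1 lists the instrument twice at day 1: once among pre-burn psychological traits ("Pain catastrophizing, SF12 MCS, DASS21, Life events checklist") and once under physical function ("SF12, work/disability questions"). The second entry is repeated at every follow-up.

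**The concern.** PCS and MCS are presented as measures of health, and the treatments are meant to improve health. A rule that rewards a fall in those scores conflicts with that aim.

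This is the only clinical-importance criterion the document gives for the SF-12, and it exists to interpret the SF-12 mixed-model results. If it were followed, its label would contradict the sign of the contrasts it is applied to: an arm that worsened by 4.5 points would be reported as clinically improved, and an arm that gained 4.5 points would not. If the analyst corrected it silently, a pre-specified rule would have been changed without a record.

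**Working it through.** **Step 1: is there anything to reproduce?** No sample size, power or alpha in section 6 is derived from the SF-12 threshold. The only figures are the range 2.5 to 4.5 and the cut-off of 4.5, which is the upper end of that range. The two agree in size, so only the direction is in question. The cited source was not available, so the size itself was not checked.

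**Step 2: the direction of benefit in the document.** Section 3.4 wants health, as measured by these scores, to improve. Section 1.5 treats reduced health as a harm. Section 6.2 names the scores as the measure of general health. Read together, a higher score is the good direction. A search of every SF-12, PCS and MCS mention found no reverse-coding, no statement that lower is better and no second threshold. The secondary objective in section 2 does use the word *reducing*, but what should fall there is pain interference, not the score. That pairing with the Brief Pain Inventory may be where the wording came from.

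**Step 3: group means.** Once higher is taken as better, no distributional assumption is needed. A mean change of +4.5 fails the written rule and a mean change of −4.5 meets it.

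**Step 4: individuals, as an illustration.** Let a patient's change be normal with mean m and SD s.

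- Written rule: P(change ≤ −4.5) = Φ((−4.5 − m)/s)
- Sign corrected: P(change ≥ 4.5) = 1 − Φ((4.5 − m)/s)
- Same label under both rules (change smaller than 4.5 either way): 1 minus the sum of the two

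The means 2.5 and 4.5 are the ends of the protocol's range. The document gives no SD of change; 8 to 12 is an assumption.

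| Mean gain m | SD s | Written rule | Sign corrected | Same label under both |
|---|---|---|---|---|
| 4.5 | 8 | Φ(−1.125) = 0.130 | 0.500 | 0.370 |
| 4.5 | 10 | Φ(−0.900) = 0.184 | 0.500 | 0.316 |
| 4.5 | 12 | Φ(−0.750) = 0.227 | 0.500 | 0.273 |
| 2.5 | 8 | Φ(−0.875) = 0.191 | 0.401 | 0.408 |
| 2.5 | 10 | Φ(−0.700) = 0.242 | 0.421 | 0.337 |
| 2.5 | 12 | Φ(−0.583) = 0.280 | 0.434 | 0.286 |

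**Step 5: how the rule responds to benefit.** At s = 10 and mean changes of 0, +2.5, +4.5 and +7, the written rule labels 32.6%, 24.2%, 18.4% and 12.5% improved. The corrected rule gives 32.6%, 42.1%, 50.0% and 59.9%. As written, the share called improved falls as the true benefit grows.

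**The case against.** The strongest reply is that this is a drafting slip with little reach. No test, responder endpoint, stopping rule or feasibility criterion uses the 4.5-point cut-off. The SF-12 analysis is a mixed model, and its estimates do not depend on the label. A reader who compares section 6.2 with section 3.4 would notice the clash. Section 6.2 also records that the trial stopped after the 24th patient, about 24/4 = 6 per arm, so a label on a secondary score will carry little weight. The first sentence is coherent by itself, since a health score can fall by an important amount; the fault lies in calling that fall an improvement. Finally, the document never states the scoring direction, and the percentages above assume an individual classification that it does not define.

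Most of this is fair and limits the size of the point. The scoring direction is an inference, and it underlies the group-mean statement too. The percentages are illustrations, and the 50% follows simply from setting the mean equal to the threshold. The missing reference assessment, time point and unit are gaps in detail, separate from the sign; the two day-1 entries may be one form listed under two domains.

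None of this rescues the rule. It is a stated threshold for a named secondary endpoint, and it gives the wrong label when followed. If the sponsor does intend reverse-coded scores, the document has to say so, and the paragraph still needs changing.

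**Conclusion.** The concern holds. The criterion for clinically significant improvement in PCS and MCS has its sign reversed relative to the protocol's own aim. A group that gains 4.5 points is not credited and a group that loses 4.5 is. Under the assumed normal model with SD 8 to 12, the share of individuals labelled improved is 13% to 23% instead of 50% at a true mean gain of 4.5, and 19% to 28% instead of 40% to 43% at a gain of 2.5. In these scenarios 27% to 41% of patients change by less than 4.5 points and receive the same label either way.

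The conclusion rests on higher scores meaning better health, which the wording of sections 1.5, 3.4 and 6.2 supports and nothing contradicts. The percentages rest also on the assumed SD and on applying the rule to individuals. The consequence is limited to how a secondary endpoint is interpreted. It should be fixed because it can reverse a reported conclusion and is cheap to correct.

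**What to change.** In section 6.2:

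1. Replace *reduction* with *change* in the sentence giving the 2.5 to 4.5 range.
2. State that higher PCS and MCS mean better health, that an increase of at least 4.5 is a clinically significant improvement, and that a decrease of at least 4.5 is a clinically significant worsening. If the scores are in fact reverse-coded, say so instead.
3. For completeness, name the reference assessment (which day-1 SF-12, pre-burn or current, or an earlier follow-up) and the follow-up time. State whether 4.5 applies to individual change or to the between-group mean difference from the mixed model.

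The cost is two or three sentences. Data collection, sample size and models stay as they are. The correction should be recorded as a change to the plan, not made silently when the results are written up.

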### **6.3 Subject Population(s) for Analysis**

We will examine effect of n-3 PUFA, Vitamin D, and n-3 PUFA+Vitamin D treatment on pain outcomes using the following populations; however, the All-randomized population will be the primary analysis performed in this study following an intention to treat paradigm.

Primary Analysis:

- All-randomized population: Any subject randomized into the study, in the group to which they were randomized, regardless of extent of study drug received (intention-to-treat).

Secondary Analyses:

- Protocol-compliant population: Any subject who was randomized and maintained  $>80\%$  study medication adherence, and no major protocol violations.

## **7 Safety and Adverse Events**

### **7.1 Definitions**

#### **Unanticipated Problems Involving Risk to Subjects or Others**

Any incident, experience, or outcome that meets all of the following criteria:

- Unexpected in nature, severity, or frequency (i.e. not described in study-related documents such as the IRB-approved protocol or consent form, the investigators brochure, etc.).
- Related or possibly related to participation in the research (i.e. possibly related means there is a reasonable possibility that the incident experience, or outcome may have been caused by the procedures involved in the research).
- Serious (as defined below) “Serious” is different than “severe” as reported in the CTC criteria that applies a grade to the AE.

### **Adverse Event**

An **adverse event** (AE) is any symptom, sign, illness or experience that develops or worsens in severity during the course of the study. Intercurrent illnesses or injuries should be regarded as adverse events. Abnormal results of diagnostic procedures are considered to be adverse events if the abnormality:

- results in study withdrawal
- is associated with a serious adverse event
- is associated with clinical signs or symptoms
- leads to additional treatment or to further diagnostic tests
- is considered by the investigator to be of clinical significance

### **Serious Adverse Event**

Adverse events are classified as serious or non-serious. A **serious adverse event** is any AE that is:

- fatal
- life-threatening
- requires or prolongs hospital stay
- results in persistent or significant disability or incapacity
- a congenital anomaly or birth defect
- an important medical event

Important medical events are those that may not be immediately life threatening, but are clearly of major clinical significance. They may jeopardize the subject, and may require intervention to prevent one of the other serious outcomes noted above. For example, drug overdose or abuse, a seizure that did not result in in-patient hospitalization, or intensive treatment of bronchospasm in an emergency department would typically be considered serious.

All adverse events that do not meet any of the criteria for serious should be regarded as **non-serious adverse events**.

### **Adverse Event Reporting Period**

The study period during which adverse events must be reported is normally defined as the period from the initiation of any study procedures to the end of the study treatment follow-up. For this study, the study treatment follow-up is defined as 30 days following the last administration of study treatment.

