### **3.9 Early Withdrawal of Subjects**

#### **3.9.1 When and How to Withdraw Subjects**

Participants may withdraw from the study at any point in time. If patients experience side effects such as gastroesophageal reflux/"heartburn", unpleasant taste that cannot be tolerated or any other unwanted effect and elect not to continue the study drug, they will be followed and included in the intention to treat analysis. Abrupt discontinuation of the study medication or comparator is not expected to affect/compromise patient safety. In other words, no wean would be needed. If patients are determined to be pregnant during the 6 weeks of drug administration (through home urine pregnancy test, or through an office based urine/serum pregnancy test) then the study drug will be discontinued, but the patients will be followed in an intention to treat fashion.

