## **4.2 Treatment Regimen**

For 6 weeks following enrollment in this study, participants will be provided with study drug or placebo. Both the n-3 PUFA and Vitamin D will be taken together once per day.

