## **4.4 Preparation and Administration of Study Drug**

Study medication, including n-3 PUFA, Vitamin D3 and comparator, will be ordered directly from the supplier and delivered to the investigational drug pharmacy (IDS) at each site. All medication will be stored in a climate controlled storage area. The containers will be labeled by the manufacturer. Each participant will receive two bottles of study medication one containing n-3 PUFA or control and another containing Vitamin D or placebo to take once daily. The fish oil/placebo will contain 168 capsules, and will have instructions to "take 4 capsules by mouth each morning for 6 weeks." The Vitamin D3/placebo will contain 42 capsules, and will have instructions that read "take 1 capsule by mouth each evening for 6 weeks." Upon discharge, the patients will be given a quantity to complete 6 week course of study medication. Lost medication will be replaced upon request and this will be dispensed by the IDS pharmacy and shipped to participant by the site coordinator. At Washington Hospital Center, an IDS pharmacy will not be used, and procedures will be developed that will enable dispensing study drug and accounting for dispensed study drug per their protocol approved by the site IRB.

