## **5.5 6 week assessment**

The goal of this assessment is to perform a comprehensive phenotypic follow-up and perform a blood draw to assess for lipid concentration, Vitamin D concentration and related gene expression (RNA), and epigenetic changes (DNA).

Outcome assessments will be performed via structured and scripted interview/survey either at the burn clinic or via telephone or via a web based survey emailed to their on file email address. Multiple methods of contacting participants may be used to best meet the needs of the participants. Average pain and itch (0-10 NRS), frequency of pain and itch during the past 24 hours at the patient's donor site, as well as average pain and itch (0-10 NRS) and frequency of pain and itch during the past 24 hours at the patient's graft site will be assessed. The condensed bleeding assessment tool will be repeated to assess for bleeding events between the 3 and 6 week timepoints. The presence of neuropathic pain symptoms (DN4, S-LANSS) will also be assessed, as well as pain and itch related interference in daily activities (Brief Pain/Itch Inventory Interference Subscales). Information regarding current medication use (both standing and PRN) and health services utilization (including burn care such as PT, OT) will also be obtained. At these time points the following assessments will also be administered: The frequency of scratching and its effect on itch related to the burn, at either the donor site or the graft site, will be evaluated. The location (Regional Pain Scale) and intensity (0-10 NRS) of pain and itch symptoms (using a modified RPS) in any locations other than the donor and graft sites will be assessed, along with the presence and severity of other somatic symptoms (e.g. headache, dizziness, and itching). General health (SF-12), depressive and anxiety symptoms (DASS), and PTSD symptoms (PSS-I) will be assessed. Sleep quality will be assessed using the MOS Sleep Scale. Global recovery after burn injury will be evaluated using a 0-100 percent improvement scale (0% = no recovery, 100% = completely recovered). Alcohol abuse is common among injured patients, and increased alcohol or drug use after trauma is likely to be related to chronic pain and itch outcomes. Quantity and frequency of alcohol and drug use will be assessed at the 24 week and 48 week follow-up time points, using questions from the TWEAK and Substance Abuse Outcomes Module.

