## **5.6 3, 6 and 12 month assessments**

Outcome assessments will be performed via structured and scripted telephone interviews. Average pain and itch (0-10 NRS), frequency of pain and itch during the past 24 hours at the patient's donor site, as well as average pain and itch (0-10 NRS) and frequency of pain and itch during the past 24 hours at the patient's graft site will be assessed. The presence of neuropathic pain symptoms (DN4, S-LANSS) will also be assessed, as well as pain and itch related interference in daily activities (Brief Pain/Itch Inventory Interference Subscales). Information regarding current medication use (both standing and PRN) and health services utilization (including burn care such as PT, OT) will also be obtained. At these time points the following assessments will also be administered: The frequency of scratching and its effect on itch related to the burn, at either the donor site or the graft site, will be evaluated. The location (Regional Pain Scale) and intensity (0-10 NRS) of pain and itch symptoms (using a modified RPS) in any locations other than the donor and graft sites will be assessed, along with the presence and severity of other somatic symptoms (e.g. headache, dizziness, and itching). General health (SF-12), depressive and anxiety symptoms (DASS), and PTSD symptoms (PSS-I) will be assessed. Sleep quality will be assessed using the MOS Sleep Scale. Global recovery after burn injury will be evaluated using a 0-100 percent improvement scale (0% =no recovery, 100% =completely recovered). Pending litigation or workman's compensation claims related to the burn injury will also be evaluated (at month 12). Alcohol abuse is common among injured patients, and increased alcohol or drug use after trauma is likely to be related to chronic pain and itch outcomes. Quantity and frequency of alcohol and drug use will be assessed at the 24 week and 48 week follow-up time points, using questions from the TWEAK and Substance Abuse Outcomes Module. Photos of both the graft site and donor site (if present) will be obtained using a standard algorithm using any available digital camera/smartphone and stored on the research database. If patients do not have access to a digital camera one will be mailed to their address with a return label, or they will have the photos taken during a follow-up clinic visit. We will also collect information about the number of servings of fish, olive oil, and any Vitamin D or fish oil supplements that have been consumed since the 6 week treatment period. Participants will be contacted at 9 months for a brief participant contact information update. This will ensure that the participant's address, phone number, and e-mail address are up-to-date for study contact purposes.

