### 7.6 Medical Monitoring

**A. Safety Monitoring Plan:** Overall safety oversight will be the responsibility of the data coordinating center PI (DCC PI). Monitoring the study (across one or more study sites) is considerably facilitated by the use of a single electronic database

which can be reviewed by the network PI, study site PI(s), and other investigators. The DCC PI will monitor for adverse events that change study risk level and this will be communicated with the independent medical monitor if needed. Adverse events at individual study sites will also be monitored by the site PI. If an

Serious AE	Death Life threatening reaction Inpatient hospitalization prolonged, or rehospitalization Persistent or significant disability/incapacity Congenital anomaly/birth defect Represents other significant hazards or potentially serious harm to research subjects (similar to "important medical event")
Expected AE	Known potential effect of the drug (based on drug description information from manufacturer) or disease process

adverse event occurs which changes the study risk level, the DCC PI will immediately report this event to the DCC IRB (UNC IRB), inform the site PI(s), and oversee the process of modifying the study at the study site(s) as appropriate to address the change in risk. The DCC PI will also provide annual reports summarizing AE data to the data coordinating center IRB (UNC IRB) and any other requesting IRB. The site PI(s) will oversee patient safety at their site, with delegation of responsibilities to other investigators and designated study personnel as appropriate. The DCC PI, together with their study site teams, will ensure that all entry criteria are met prior to the initiation of the protocol, and that all study procedures and reporting of adverse events are performed according to the protocol. Serious adverse events (SAE's) will be monitored by the study site investigative teams in real time throughout the trial.

**Patient monitoring:** An adverse event is any physical or clinical change experienced by the patient. This includes the onset of new symptoms and the exacerbation of pre-existing conditions. Adverse event assessments will be performed according to the following schedule:

**Adverse event monitoring after discharge:** Adverse events will be assessed at each patient contact (telephone or text-messaged/mailed survey), which will occur weekly while on the study drug.

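### Adverse events are reportable for 30 days after the last dose, but no contact is scheduled between week 6 and month 3, and weekly adverse event contact is not assured after early stopping

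*Combined protocol and SAP*

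**What the plan says.** Section 7.1 (Adverse Event Reporting Period) sets the end of AE reporting: "the study treatment follow-up is defined as 30 days following the last administration of study treatment".

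Section 7.6 gives the contact schedule after discharge: "Adverse events will be assessed at each patient contact (telephone or text-messaged/mailed survey), which will occur weekly while on the study drug". Sections 3.1 and 3.5 likewise place the safety calls and AE surveys in the treatment period. Section 5.4 adds a staff contact at 3 weeks that collects AEs and includes a bleeding assessment. Section 5.5 has the last structured bleeding enquiry: "The condensed bleeding assessment tool will be repeated to assess for bleeding events between the 3 and 6 week timepoints". Section 7.2 requires AE questioning at every contact.

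After week 6, the next contact in section 3.1, in the measures table of section 5.1 and in section 10.3 is at 3 months. Section 5.6 describes that call: "Outcome assessments will be performed via structured and scripted telephone interviews". Its long list of items names neither AEs nor the bleeding tool.

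Under section 3.9.1, participants who have unwanted effects and "elect not to continue the study drug, they will be followed and included in the intention to treat analysis". Section 3.9.2 adds that those who withdraw because of side effects are followed until the symptoms resolve or are judged unrelated.

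**The concern.** Safety is part of the primary objective. Under section 6.2 it is judged from AEs tabulated by arm and reviewed descriptively, with no inferential comparison. Such a table is only as good as the completeness and evenness of the ascertainment behind it. If part of the declared reporting period has no planned enquiry, few recorded events may mean few events or few questions. If participants who stop drug are asked less often than those who continue, and stopping differs between arms, the arms may not be observed equally. Bleeding shows the point: section 1.5 names it as a possible effect of fish oil, yet structured bleeding enquiry ends at week 6.

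**Working it through.** **1. Course length.** Section 4.4 states "The fish oil/placebo will contain 168 capsules", at 4 per day: 168 / 4 = 42 days. The Vitamin D bottle holds 42 capsules, labelled "take 1 capsule by mouth each evening for 6 weeks": 42 / 1 = 42 days. Section 4.2 starts the clock at enrollment: "For 6 weeks following enrollment in this study, participants will be provided with study drug or placebo".

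**2. List of contacts.** The payments in section 10.3 give a complete list of paid contacts: 35 (enrollment) + 5 × 10 (weekly) + (20 + 45 + 10) (6 weeks) + 2 × 25 (3 and 6 months) + 10 (9 months) + 30 (12 months) = 250. This reproduces the stated maximum of $250. No paid contact lies between week 6 and month 3.

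**3. Completers.** Enrollment is within 72 hours of the burn in sections 3.1 and 5.1 and within 96 hours in section 3.6, so the first dose is taken here as day 0 to 4 after the burn. Last dose = first dose + 41. Window closes = last dose + 30. The documents give no visit windows, so I take the 6-week visit as day 42 and 3 months as day 84 to 92 after the burn.

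| First dose | Last dose | Window closes | 6-week visit relative to last dose | Days from window close to 3-month call (day 84 / day 92) |
|---|---|---|---|---|
| Day 0 | Day 41 | Day 71 | 1 day after | 13 / 21 |
| Day 4 | Day 45 | Day 75 | 3 days before | 9 / 17 |

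The 6-week visit reaches at most the first post-dose day, so 29 to 30 of the 30 post-dose days have no planned contact. With dosing from the day of enrollment, the AE period is 42 + 30 = 72 days, and the uncovered share is 29/72 to 30/72, or 40% to 42%. The 3-month call comes 9 to 21 days after the window closes, which is 39 to 51 days after the last dose.

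**4. Early stoppers.** Count from first dose = day 0. A participant whose last dose is on treatment day d takes it on day d − 1, and the window closes on day d + 29.

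- The week-3 contact (day 21) is after the last dose and inside the window if d − 1 < 21 ≤ d + 29, that is, d = 1 to 21.
- The week-6 contact (day 42) qualifies if d − 1 < 42 ≤ d + 29, that is, d = 13 to 42.
- Together they cover every stop day from 1 to 42. If contacts are counted from the burn and the first dose is on day 3 or 4, only stop days 40–42 or 39–42 have neither.

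Take a stop on treatment day 14: last dose day 13, window closes day 43. Weekly contacts fall on days 7, 14, 21, 28, 35 and 42. Week 2 coincides with the stop. Weeks 3 and 6 remain under sections 5.4 and 5.5. Weeks 4 and 5 (days 28 and 35) are the contacts that section 7.6 does not assure.

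**The case against.** The strongest reply is that collection is thinner after week 6 but not absent. Section 7.2 requires AE questioning at every contact, so the 3-month call collects AEs even though section 5.6 does not repeat the rule. An event inside the window but elicited later can still be recorded. Section 7.6 gives participants a toll-free number and asks them to call about any change in health. All of this stands, and it means that the weakness for completers is reliance on spontaneous report and longer recall. It does not supply a planned contact inside the window or a stated recall period.

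Section 4.5, read literally, puts weekly surveys after the treatment period, which would fill the gap. Those surveys ask about missed doses, so the phrase most plausibly means after inpatient treatment. It still conflicts with sections 3.1, 3.5, 7.6 and 10.3.

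A reader might infer that early stoppers have no AE contact within their window, or that a day-14 stopper loses four of six weekly assessments. The documents do not support either: stoppers stay in follow-up, and the week-3 and week-6 contacts do not depend on taking drug. Section 10.3 also describes the weekly contacts without tying them to drug use, so the plan is ambiguous here. A reader might also infer a bias in favour of the less well tolerated drug. No discontinuation or AE rate by arm is given, and the event that prompts stopping comes before any loss of contact, so that direction is not shown.

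**Conclusion.** The point holds in two parts. For completers, the 30-day post-dose part of the AE period has essentially no planned AE contact (29 to 30 of 30 days), and the next call falls after the window has closed under every reading tried. For early stoppers, at least one fixed contact falls in the window for nearly every stop day, but sections 3.5 and 7.6 do not assure the remaining weekly AE contacts, about two for a day-14 stopper. Ascertainment may therefore be unequal between stoppers and completers; whether that biases the comparison of arms, in which direction and by how much, cannot be derived.

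The figures rest on a first dose 0 to 4 days after the burn, 3 months taken as day 84 to 92, no visit windows, and section 4.5 read as referring to inpatient treatment.

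**What to change.** - In section 7.6, state that weekly AE contact runs through week 6 for all randomized participants, whether or not study drug has been stopped. Reconcile section 4.5 with sections 3.1, 3.5, 7.6 and 10.3.
- Send everyone, early stoppers included, one automated RedCap AE survey with bleeding items about 30 days after the last dose.
- At the 3-month call, ask about AEs since the last completed AE contact and record onset dates, so that events inside the window can be identified. A recall period fixed as week 6 to 30 days after the last dose would not work: counted from enrollment, the window of anyone stopping on day 13 or earlier closes by day 42, so that period would be empty or run backwards.

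The cost is a wording change, one survey in an existing system, a few minutes on a planned call and a slight added burden for participants. Section 6.2 records that the study was terminated after the 24th patient was enrolled. Where these windows have already passed, the contacts cannot be recovered; the sponsor should disclose the gap when reporting safety and apply the schedule to the planned larger trial.
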